## 12.3 Expected Adverse Events/Serious Adverse Events (AE/SAE)

The following is a list of expected complications related to the administration of any research procedure including pre- and post-operative complications associated with either surgical procedure or the use of general anaesthetic.

---

This are categorised as Common (>1/100), Uncommon (~1/1000) and Rare ~1/10,000

### **Common**

- Dural tear
- CSF leak
- Epidural Haematoma
- Neurological root injury (including C5 Palsy)
- Worsening myelopathy
- Post-operative red eye
- Swallowing difficulties
- Hoarse Voice
- Neck Pain
- Adjacent segment disease
- Drowsiness, confusion or restlessness
- Nausea and/or vomiting
- Soft tissue infection
- Urinary tract infection
- Respiratory infection

### **Uncommon**

- Inadequate Decompression
- Spinal cord injury
- Injury to the mouth or teeth from intubation or the breathing tube
- Myocardial Infarction
- Respiratory problems

### **Rare**

- Blindness
- Vertebral artery injury
- Wrong level surgery
- Anaphylaxis
- Stroke
- Cardiac Arrest

For laminectomy only procedures, as outlined in the trial premise, post procedural deformity or instability is possible, but the frequency and significance will be defined by this trial.

For laminectomy and fusion, the insertion of metal work carries the following additional uncommon risks:

- Metal work malposition
- Metal work failure
- Failure of bony fusion

Whilst CRFs will document each adverse event specifically, it is planned that for analysis, this will be aggregated into the consensus derived categories of surgical complications for DCM, by Tetreault et al 2019 .

## 12.4 Evaluation of adverse events

The Sponsor expects that adverse events are recorded from the point of Informed Consent regardless of whether a participant has yet received a research procedure. Individual adverse events should be evaluated by the investigator. This includes the evaluation of its seriousness, and any relationship between the investigational medicinal product(s) and/or concomitant therapy and the adverse event (causality).

### 12.4.1 Assessment of seriousness

Seriousness is assessed against the criteria in section 12.1.4. This defines whether the event is an adverse event, serious adverse event or a serious adverse reaction

### 12.4.2 Assessment of causality

**Definitely:** A causal relationship is clinically/biologically certain. **This is therefore an Adverse Reaction**

**Probable:** A causal relationship is clinically / biologically highly plausible and there is a plausible time sequence between onset of the AE and administration of the research procedure and there is a reasonable response on withdrawal. **This is therefore an Adverse Reaction.**

**Possible:** A causal relationship is clinically / biologically plausible and there is a plausible time sequence between onset of the AE and administration of the research procedure **This is therefore an Adverse Reaction.**

**Unlikely:** A causal relation is improbable and another documented cause of the AE is most plausible. **This is therefore an Adverse Event.**

**Unrelated:** A causal relationship can be definitely excluded and another documented cause of the AE is most plausible. **This is therefore an Adverse Event.**

Unlikely and Unrelated causalities are considered NOT to be related to the intervention  
Definitely, Probable and Possible causalities are considered to be related to the intervention

A pre-existing condition must not be recorded as an AE or reported as an SAE unless the condition worsens during the trial and meets the criteria for reporting or recording in

the appropriate section of the CRF.

#### 12.4.3 Clinical assessment of severity

Mild: The participant is aware of the event or symptom, but the event or symptom is easily tolerated

Moderate: The participant experiences sufficient discomfort to interfere with or reduce his or her usual level of activity

Severe: Significant impairment of functioning; the subject is unable to carry out usual activities and / or the participant's life is at risk from the event.

#### 12.4.4 Recording of adverse events

Adverse events and adverse reactions should be recorded in the medical notes and the appropriate section of the CRF and/or AE/AR log. Serious Adverse Events and Serious Adverse Reactions should be reported to the sponsor as detailed in section 12.5.

### **12.5 Reporting serious adverse events**

Each Principal Investigator needs to record all adverse events and report serious adverse events to the Chief Investigator using the trial specific SAE form within 24 hours of their awareness of the event.

The Chief Investigator is responsible for ensuring the assessment of all SAEs for expectedness and relatedness is completed and the onward notification of all SAEs to the Sponsor immediately but not more than 24 hours of first notification. The sponsor has to keep detailed records of all SAEs reported to them by the trial team.

The Chief Investigator is also responsible for prompt reporting of all serious adverse event findings to the relevant authorities of each concerned Member State if they could:

- adversely affect the health of participants
- impact on the conduct of the trial
- alter the risk to benefit ratio of the trial

The completed SAE form can be emailed. Details of where to report the SAE's can be found on the POLYFIX DCM SAE form and the front cover of the protocol.

### **12.6 Reporting of Suspected Unexpected Serious Adverse Reactions (SUSARs)**

All suspected adverse reactions which occur in the concerned trial, and that are both unexpected and serious (SUSARs) are subject to expedited reporting.

#### 12.6.1 Who should report and whom to report to?

The Sponsor delegates the responsibility of notification of SUSARs to the Chief Investigator. The Chief Investigator must report all the relevant safety information previously described, to the:

- Sponsor
- Ethics Committee in the concerned member states

The Chief Investigator shall inform all investigators concerned of relevant information about SUSARs that could adversely affect the safety of participants.

## 12.6.2 When to report?

### 12.6.2.1 Fatal or life-threatening SUSARs

All parties listed in 12.6.1 must be notified as soon as possible but no later than **7 calendar days** after the trial team and Sponsor has first knowledge of the minimum criteria for expedited reporting.

In each case relevant follow-up information should be sought and a report completed as soon as possible. It should be communicated to all parties within an additional **8 calendar days**.

### 12.6.2.2 Non-fatal and non-life-threatening SUSARs

All other SUSARs and safety issues must be reported to all parties listed in 12.6.1 as soon as possible but no later than **15 calendar days** after first knowledge of the minimum criteria for expedited reporting. Further relevant follow-up information should be given as soon as possible.

## 12.6.3 How to report?

### 12.6.3.1 Minimum criteria for initial expedited reporting of SUSARs

Information on the final description and evaluation of an adverse reaction report may not be available within the required time frames for reporting. For regulatory purposes, initial expedited reports should be submitted within the time limits as soon as the minimum following criteria are met:

- a) a suspected research procedure
- b) an identifiable participant (e.g. trial participant code number)
- c) an adverse event assessed as serious and unexpected, and for which there is a reasonable suspected causal relationship
- d) an identifiable reporting source

and, when available and applicable:

- 
- an unique case identification (i.e. sponsor's case identification number)

### 12.6.3.2 Follow-up reports of SUSARs

In case of incomplete information at the time of initial reporting, all the appropriate information for an adequate analysis of causality should be actively sought from the reporter or other available sources. Further available relevant information should be reported as follow-up reports.

In certain cases, it may be appropriate to conduct follow-up of the long-term outcome of a particular reaction.

## 13 **Evaluation of Results (Definitions and response/evaluation of outcome measures)**

### 13.1 **Response criteria**

#### 13.1.1 Neurological function

To be measured by the mJOA scale at baseline, 6-, 12- and 24-months post-surgery.

### 13.1.2 Pain

To be measured by the BPI, numeric rating score for average pain scale at baseline, 6-, 12- and 24-months post-surgery.

### 13.1.3 Radiological Outcomes

Cervical spine X-Rays (flexion/extension lateral views) will be conducted at baseline, post-operatively, 6-, 12- and 24-months post-surgery. Pre-operative X-Rays will assess any movement and alignment. Post-operative X-Rays will assess for alignment, fusion and movement.

### 13.1.4 Quality of life

Participant quality of life will be assessed at baseline, 6-, 12- and 24-months post-surgery. Both will be assessed by the SF36v2 survey.

## 14 **Storage and Analysis of Samples**

POLYFIX DCM will not involve neither the collection nor storage of any samples.

## 15 **Statistics**

### 15.1 **Statistical methods**

The primary objective will be evaluated using a two-sided t-test at a 5% significance level. The trial is powered to detect a 1-point difference in the mJOA scale between arms.

The ordering of subsequent endpoints for formal hypothesis testing will be:

1. BPI Pain
2. Neck Disability Index
3. PCS component of the SF-36
4. MCS component of the SF-36
5. mJOA (Upper Limb, Motor Score)
6. mJOA (Lower Limb, Motor Score)

A range of MCID for these endpoints have been proposed using a range of methods. As secondary endpoints the trial is not implicitly powered to detect a specific difference, and instead analysis will estimate the difference. However, in order to recognise what is considered meaningful in advance, the following MCID are agreed based on the available literature; BPI 20mm, NDI 8 points, SF36 PCS 5 points, MCS SF36 4 points, mJOA Subdomain scores 1 point.

A descriptive analysis of the following secondary outcome measures will be provided:

- SF36v2 (Quality of life) Score
- EQ5D-5L
- Neck Disability Index (NDI)
- Brief Pain Inventory (BPI)
- Douleur Neuropathique 4(DN4)
- Michigan Body Map (Pain Location)
- Complications (including surgical site infection, wound breakdown, instrument failure)
- Adverse Events

- Cervical X-Rays (Deformity, Fusion, Movement)
- Neurological examination
- Myelopathy.org Symptom Inventory

A predefined subgroup analysis of the following variables will take place:

- Number of levels treated
- Presence / Amount of movement pre-operatively (>1mm subluxation on flexion/extension X-Ray)
- Presence of auto-fusion at 1 or more cervical level pre-operatively (radiological evidence of spontaneous fusion between two adjacent vertebrae)
- Presence of Kyphosis (C2-C7 Cobb Angle <0°)
- Presence of Cervical Ossification of Posterior Longitudinal Ligament
- Previous Cervical Spine Surgery
- Age

The following baseline covariates, in addition to the baseline value of the endpoint, will be used to adjust all comparisons:

- Time to onset
- Smoking status (yes/no)
- Age
- Psychiatric comorbidities (yes/no)
- Impaired Gait (yes/no)

A detailed statistical analysis plan will be produced before the final data base lock.

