### 9.3 Treatment Assignment and Randomisation Number

An online randomisation system will be used to assign participants in a 1:1 ratio to treatment with either laminectomy alone or laminectomy and fusion. Stratified blocked randomisation will be used stratifying by baseline mJOA (<12 vs >=12), age (<60 years vs >=60 years) and time to onset (>6 months vs <=6 months); random block size will be used.

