### **15.3 Number of Participants to be enrolled**

POLYFIX DCM plans to include 394 participants in total. The pilot phase aims to assess at least 40 participants.

The minimum clinically important difference (MCID) for the mJOA is estimated to be between 1 and 2 points. As the mJOA is demonstrated to improve greater than the MCID with surgery (including laminectomy or laminectomy with fusion) alone, with the amount of change linked to the pre-operative baseline. Consequently, in consensus with patients, we have determined a MCID for the mJOA of 1 point for additional gains. This is in keeping with the trial design of recent DCM RCTs, CSM Protect NCT01257828 and RECEDE-Myelopathy (EducaCT number: 2017-004856-41). This has been modelled to ensure statistical power across all baseline scenarios.

On this basis, a total sample size of 394 participants under equal randomisation will provide 90% power (accounting for 10% drop out rate) to detect a change of 1 from baseline on the mJOA scale (assuming a standard deviation [SD] of 2.89), using a two-sided t-test at a 5% significance level.

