### **15.5 Procedure to account for missing or spurious data**

The data will be analysed in two populations, a safety population that includes all patients who have consented to the trial, and a full analysis population that include all patients who are randomised. Groups will be allocated using the ITT principle that looks at which arm they were randomised to, disregarding subsequent deviations from protocol.

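### Section 15.1 names a t-test for the primary endpoint but adjusts all comparisons for covariates, and names no model, so the primary estimate and p-value are not uniquely defined

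*Protocol*

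**What the plan says.** Protocol section 15.1 opens with the primary test: "The primary objective will be evaluated using a two-sided t-test at a 5% significance level". Later in the same section comes the adjustment rule: "The following baseline covariates, in addition to the baseline value of the endpoint, will be used to adjust all comparisons". The list that follows is time to onset, smoking status, age, psychiatric comorbidities and impaired gait. The primary comparison is not exempted, and no regression or analysis-of-covariance model is named.

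Section 9.3 describes the allocation: "Stratified blocked randomisation will be used stratifying by baseline mJOA (<12 vs >=12), age (<60 years vs >=60 years) and time to onset", at 1:1.

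Section 15.3 sizes the trial "using a two-sided t-test at a 5% significance level", with an SD of 2.89, 90% power and 10% drop-out. It includes no covariate term. It describes the target as "to detect a change of 1 from baseline on the mJOA scale", whereas section 8.5.1 describes a between-arm difference of 1 point at 24 months. Section 15.3 also says that the amount of mJOA change depends on the pre-operative baseline.

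**The concern.** In its ordinary sense a two-sample t-test adjusts for nothing, while the adjustment rule covers every comparison. A statistician could follow either sentence and claim to have followed the protocol, and would report different primary results. A detailed SAP is promised only before final database lock, and the clinical teams and patients know the allocation. It is better that the choice does not remain open that long.

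The choice also affects how well the analysis fits the design. Stratified allocation balances the arms on baseline mJOA, age and time to onset, which reduces the true variability of the treatment difference when these factors predict outcome. An unadjusted t-test leaves that reduction out of its standard error. The adjusted analysis takes it in, because all three factors are in the section 15.1 adjustment set when the endpoint is mJOA.

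**Working it through.** **Inputs from the protocol.** Difference 1 point, SD 2.89, two-sided 5%, power 90%, drop-out 10% (section 15.3); 1:1 allocation and three binary stratifiers, hence 8 strata (section 9.3). The share of outcome variance explained by the stratifiers or covariates (R²) is not given and is assumed below.

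**1. Reproduce 394.** Normal approximation: n per arm = 2 × (1.96 + 1.2816)² × 2.89² / 1² = 175.5, so 176. The exact two-sample t-test (non-central t) gives 176.5, so 177 per arm and 354 in total. Then 354 / 0.90 = 393.3, rounded up to 394. The stated figure is reproduced exactly, with no covariate adjustment.

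**2. Precision and power as sized.** SE = 2.89 × √(2/177) = 0.307. The 95% half-width is 1.96 × 0.307 = 0.60 points. Power is about Φ(1/0.3072 − 1.96) = Φ(1.295) = 90%.

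**3. Unadjusted t-test after stratified allocation.** If the strata explain a share R² of the variance, the reported SE stays near 0.307 while the true SE is about 0.307 × √(1 − R²). Hence type I error = 2 × [1 − Φ(1.96/√(1 − R²))] and power = Φ(1.295/√(1 − R²)). For the adjusted model, the SD becomes 2.89 × √(1 − R²) with the same 177 per arm.

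| Assumed R² | t-test type I error | t-test power | Adjusted half-width | Adjusted power |
|---|---|---|---|---|
| 0 | 5.0% | 90% | 0.60 | 90% |
| 0.10 | 3.9% | 91% | 0.57 | 93% |
| 0.20 | 2.8% | 93% | 0.54 | 95% |
| 0.30 | 1.9% | 94% | 0.50 | 97% |

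**4. Check by simulation.** 354 evaluable participants, 8 strata, random blocks of 2, 4 and 6, 3,000 runs per scenario. Here R² belongs to the continuous factors and the strata are cut from them, so stratification captures only part of it and the effect is smaller than the formula gives at the same R².

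- R² = 0: t-test type I error 5.3%, within simulation error of 5%.
- R² = 0.25: type I error 3.2%; mean reported SE 0.307 against a true SD of about 0.28, roughly 9% too wide; power 92% for the t-test and 96% adjusted.
- R² = 0.40: type I error 2.1%; 0.307 against about 0.26, 14% to 19% too wide; power 93% and 99%.
- The adjusted model held 4.9% to 5.5% type I error throughout.

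**5. Final score or change score.** Write the change-score model as Y − B = a + bT + cB, where B is baseline mJOA and T is arm. Rearranged, Y = a + bT + (c + 1)B. The treatment coefficient b, its SE and its p-value are identical. The scale therefore matters for an unadjusted t-test but not once baseline mJOA is a covariate. It still decides what 2.89 means: with baseline correlation r, and equal SDs at the two times, the adjusted SD is 2.89 × √(1 − r²) if 2.89 is the SD of the 24-month score, or 2.89 × √((1 + r)/2) if it is the SD of change. For r from 0.3 to 0.6 (assumed), power at 177 per arm is 93% to 98% in the first case and 95% to 98% in the second.

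**The case against.** The strongest reply is that the two sentences can be reconciled. The test of a treatment coefficient in a linear model is itself a two-sided t-test, and section 15.1 never says unadjusted or two-sample. Sizing a trial on a simple test does not oblige the analysis to be simple. This reading is coherent and probably close to what was intended. But the text does not state it: no model is named, and the only calculation that uses the phrase is the plain two-sample one. The reply shows that the repair is easy, not that it is unnecessary.

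Four stronger inferences are tempting, and the document does not support them.

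- *The error bars are wrong.* This holds only if the test is run unadjusted and the stratifiers are prognostic. Section 15.3 says as much for baseline mJOA, in terms of change, but gives no size.
- *False positives are inflated or the trial is underpowered.* The error runs the other way, and 90% power is met under either analysis.
- *A t-test contradicts section 15.5*, which defines "a full analysis population that include all patients who are randomised". Naming a population does not say how missing 24-month values are handled. That is normally left to the SAP, and a single-time-point adjusted model would leave out the same participants.
- *The primary endpoint itself is unsettled.* Section 7 and section 8.5.1 agree on mJOA at 24 months, and section 8.5.1 on a between-arm difference. Only the sizing sentence in section 15.3 speaks of change from baseline.

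A choice made after results are seen is partly guarded against: the SAP is due before lock, and assessors of the primary outcome are blinded. In an open-label trial some residual concern is fair.

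**Conclusion.** The point holds in a limited form. Section 15.1 supports two primary analyses and names a model for neither, so the confirmatory estimate, interval and p-value are not uniquely defined. That follows from the text alone.

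The statistical cost of the unadjusted version is conditional. With an assumed R² of 10% to 30% for the strata, type I error would be about 3.9% to 1.9%, and the interval would be wider than it need be (half-width 0.60 against 0.57 to 0.50). This is lost precision in a conservative direction. The wording about change from baseline in section 15.3 is a secondary defect: it leaves open which SD 2.89 is, but has no effect on a baseline-adjusted result. Rating: should be fixed.

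**What to change.** In section 15.1, replace the t-test sentence with:

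> The primary analysis is a linear model of 24-month mJOA on treatment arm, adjusted for baseline mJOA, age, time to onset and the other listed covariates, with a two-sided 5% test of the treatment coefficient.

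In section 15.3, describe the t-test as the basis of the sample size only, reword the target as a between-arm difference of 1 point at 24 months, and state whether 2.89 is the SD of the 24-month score or of the change.

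Optionally, add baseline mJOA to the models for the secondary endpoints. It is a stratification factor, but for BPI, NDI and the SF-36 components the baseline value of the endpoint is a different measure.

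The cost is protocol wording, carried through to the SAP. Every covariate is already collected at screening or baseline (sections 11.3.1 and 11.4), and 394 is unchanged. The change should be made before anyone involved in the choice sees outcome data by arm.

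### Section 15.1 gives the primary comparison both as a two-sided t-test and as covariate-adjusted, without saying which is primary; the unadjusted test would be valid but conservative

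*Protocol*

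**What the plan says.** Section 15.1 opens with the only sentence on how the primary objective is tested: "The primary objective will be evaluated using a two-sided t-test at a 5% significance level". Section 15.3 uses the same test for the sample size: "a total sample size of 394 participants under equal randomisation will provide 90% power (accounting for 10% drop out rate"), for a 1-point effect with SD 2.89, "using a two-sided t-test at a 5% significance level". There the effect is worded as a change from baseline, whereas the primary objective (Section 8.5.1) is a between-arm difference in the mJOA at 24 months.

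Section 15.1 ends with a second rule: "The following baseline covariates, in addition to the baseline value of the endpoint, will be used to adjust all comparisons". The list is time to onset, smoking status, age, psychiatric comorbidities and impaired gait.

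Two other statements bear on the choice. Section 9.3 randomises in blocks, "stratifying by baseline mJOA (<12 vs >=12), age (<60 years vs >=60 years) and time to onset (>6 months vs <=6 months"). Section 15.3 describes mJOA improvement after surgery "with the amount of change linked to the pre-operative baseline".

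**The concern.** A two-sample t-test takes no covariates, and a comparison adjusted for six baseline variables is a different estimator with a different standard error and p-value. The adjustment rule covers every comparison, so it includes the primary one, yet the sentence on the primary objective and the sample size both point to the unadjusted test. The change-from-baseline wording in Section 15.3 adds a third candidate, a t-test on change scores.

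What is at stake is that the one confirmatory test could be carried out in more than one way, each defensible from the text. If the unadjusted version is used, precision already paid for in baseline data and stratification is lost. Stratified blocks balance the arms on baseline mJOA, age and time to onset, so variation between strata largely drops out of the estimated difference. The t-test's standard error still counts it.

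**Working it through.** **Inputs from the protocol.** Difference 1 point, SD 2.89, two-sided 5%, 90% power, 10% dropout, 394 in total (Section 15.3); 1:1 allocation and three binary strata, hence 8 cells (Section 9.3).

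**Assumed, because the protocol does not give them.** Correlation r between baseline and 24-month mJOA, 0.3 to 0.6; block sizes; share of patients with baseline mJOA below 12.

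**1. The plan's own figure.** The noncentral t calculation for 1/2.89 gives 176.5, so 177 per arm and 354 evaluable. 354/0.9 = 393.3, so 394. It reproduces exactly, with no allowance for covariates.

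**2. Precision by formula, 2.89 read as the SD of the 24-month score.** The 95% half-width is 1.96 × SD × √(2/177). Unadjusted, this is 1.96 × 2.89 × 0.1063 = 0.60. Adjusting for baseline gives a residual SD of 2.89 × √(1 − r²):

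| r | residual SD | half-width | power for 1 point | excess width of the t-test interval |
|---|---|---|---|---|
| 0.3 | 2.76 | 0.57 | 92.5% | 0.602/0.574, about 5% |
| 0.5 | 2.50 | 0.52 | 96.3% | 0.602/0.521, about 15% |
| 0.6 | 2.31 | 0.48 | 98.2% | 0.602/0.482, about 25% |

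The unadjusted formula power is 90.1%. That figure takes no account of stratification, so the fair comparison is in step 4.

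**3. The same with 2.89 read as the SD of change.** With equal variances the adjusted SD is 2.89 × √((1 + r)/2), that is 2.33, 2.50 and 2.58 for r = 0.3, 0.5 and 0.6. Half-widths are 0.49, 0.52 and 0.54, all below 0.60, with power of about 98%, 96% and 95%. The gain now shrinks as r rises, but adjustment still gives the narrower interval.

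The choice of outcome also matters by itself. If 2.89 is the SD of the score, change has SD 2.89 × √(2(1 − r)). At r = 0.3 that is 3.42, and a t-test on change has about 79% power.

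**4. Simulation under stratified blocks.** 354 patients, 8 strata, about 4,000 trials per scenario, 24-month score as outcome, age and time to onset given no effect. Results were checked for block sizes of 4 or 6 and of 2, 4 or 6, and for about half or about 20% of patients below the mJOA cut:

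| | r = 0.3 | r = 0.5 | r = 0.6 |
|---|---|---|---|
| t-test type I error | 4.3–5.0% | 3.1–3.9% | about 3% |
| t-test power, 1 point | 90–91% | about 92.5% | about 93% |
| adjusted power, 1 point | 92–93% | 96–97% | about 98% |
| disagreement on significance, 1 point | about 3% | about 5% | up to 7% |
| disagreement on significance, 0.6 points | about 7% | about 15% | 21–23% |

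The adjusted model keeps its type I error at about 5% throughout.

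**The case against.** The strongest reply is that the two sentences can be read together. The adjustment rule has no exception, the coefficient for arm in a linear model is itself tested with a two-sided t-test, and Section 15.1 does not say two-sample. On that reading the protocol already specifies one adjusted analysis. The reading is possible, but the text does not state it, and the unadjusted calculation in Section 15.3 points the other way.

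A second reply is that a detailed analysis plan is promised before database lock, and that attaching covariates to a test is routine content for it. That would carry weight if the protocol had left the matter open. Instead it makes both statements, so a plan that adopts an unadjusted test departs from one of them.

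Three stronger readings are tempting, and the documents do not support them:

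- *The plan ignores baseline mJOA and the strata.* It does not. The adjustment list, with the baseline value of the endpoint, covers all three stratification factors. Only the t-test sentence, read alone, leaves them out, and a t-test on change would still use baseline.
- *The primary test is invalid or inflates false positives.* The unadjusted test errs on the conservative side. Its planned power for 1 point is met on the 24-month score with SD 2.89.
- *The interval is too wide, full stop.* That applies to one of the candidate analyses, and at r = 0.3 the excess is only about 5%.

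It is also fair that the larger disagreement rates arise at 0.6 points, below the protocol's 1-point target.

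**Conclusion.** The point stands as an unresolved specification. Section 15.1 does not say whether the primary analysis is the unadjusted t-test or the adjusted comparison, and Section 15.3 blurs whether the outcome is the 24-month score or the change. If the unadjusted test is used, the cost is a few points of power, at most about 5 at 1 point on these assumptions, and a true type I error somewhat below 5%. Depending on the true difference, the choice would also change the verdict on significance in a small to moderate share of trials.

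The direction follows from baseline being prognostic, which Section 15.3 itself says. The size rests on an assumed correlation of 0.3 to 0.6, assumed block sizes and an assumed split at the mJOA cut. The sample size is correct for the test it names. This is a should-fix, not a threat to the trial's validity.

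**What to change.** Replace the t-test sentence in Section 15.1 with:

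> *The primary analysis is the adjusted mean difference between arms in 24-month mJOA, with 95% CI and a two-sided 5% test of the arm coefficient, from a linear model with arm, continuous baseline mJOA, age, time to onset and the other covariates listed below. The unadjusted two-sample t-test is supportive.*

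In Section 15.3, keep 394, describe the unadjusted calculation as conservative, and say whether 2.89 is the SD of the 24-month score or of the change. Carry the same single analysis into the statistical analysis plan.

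The cost is about two sentences. Every covariate is already collected at screening or baseline, so no extra data or patients are needed.
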